5.5 Modification of Study Treatment

As described in the protocol (Section 6.8), peanut OIT doses may be adjusted by the study physician if the subject is unable to tolerate the scheduled dose increase. If such a dose modification occurs, the subject will return all unused capsules of study medication during the dose adjustment visit, and be dispensed capsules at the adjusted dose level.

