At the physician's discretion, temporary dose reductions, ranging from a 1-step decrement (i.e., to the previous dose) to approximately half of the current dose level (to the nearest feasible available whole dose), can be instituted while subjects are suffering from symptoms of an upper respiratory infection or influenza, or during menses. If the dose is reduced by more than 1 step or for more than 3 days, the subject is to return to the CRC within 7 days of the dose-reduction for dose re-escalation under direct observation. If the reduction in dose is maintained for ≤ 3 days, then the pre-reduction dose may be resumed directly. For dose reductions of 1 dose level maintained for ≤ 3 days, whether dose re-escalation is to occur at home or in the CRC is at the investigator's discretion. If the reduction in dose is maintained for ≥ 3 days, the subject will have his or her 2-week escalation schedule reset to maintain the new dose for a 2-week period prior to re-escalating in a bi-weekly stepwise fashion.

Doses may also be withheld at the investigator's discretion, in response to an AE, whether the AE is assessed to be treatment-related or not. If doses are withheld for this, or any, reason, the rules for missed peanut OIT doses (Section 6.7) apply.

Subjects may develop symptoms during dosing for the build-up phase. The investigator's judgment will be required to determine the best course of action with possible actions being the following:

- Continue with daily home dosing
- Continue the same daily dose for the rest of the 2-week interval, with 50% of the dose split between doses given 8-12 h apart
- Return for repeat dosing in Clinical Research Center

- Return for dosing of previously tolerated dose (without escalation) in Clinical Research Center
- Discontinuation of dosing

If a subject has a dose escalation in the Clinical Research Center without symptoms, the action should be to continue per protocol with daily home dosing of the tolerated dose with the next escalation visit to the Clinical Research Center 2 weeks later.

If the subject experiences only oral/pharyngeal pruritus during the administration of the daily dose, then the same dose can be repeated the next day at home and continued throughout the interval unless other symptoms begin to develop (see below).

For *mild symptoms*, defined as:

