- Skin limited (few) or localized hives, swelling (e.g., mild lip edema), skin flushing (e.g., few areas of faint erythema) or pruritus (mild, e.g., causing occasional scratching)
- Respiratory rhinorrhea (e.g., occasional sniffling or sneezing), nasal congestion, occasional cough, throat discomfort
- GI mild abdominal discomfort (including mild nauseas), minor vomiting (typically a single episode) and/or a single episode of diarrhea

The action should be either to repeat the dose the next day (Day 2) at home or to have the subject return to the Clinical Research Center the next day (Day 2) for a repeat of the previous day's dose or the last tolerated dose (at the physician's discretion). If the dose is tolerated, then the subject will continue on that dose and return at the normal interval. If the dose causes mild symptoms again, then the subject will return to the Clinical Research Center (Day 3) and be given the last tolerated dose (i.e., a 1-step dose reduction) or a 2-step dose reduction. If tolerated, the subject will continue on this dose for the normal time interval. If mild symptoms recur, a further 1-2-step reduction should be administered the next day (Day 4) in the CRC. If tolerated then that dose should be continued for 2 weeks. If not tolerated, revert to a lower dose.

If *moderate symptoms* occur, defined as:

- Skin systemic hives (e.g., numerous or widespread hives), swelling (e.g., significant lip or face edema), pruritus causing protracted scratching, more than a few areas of erythema or pronounced erythema
- Respiratory throat tightness without hoarseness, persistent cough, wheezing without dyspnea
- GI persistent moderate abdominal pain/cramping/nausea, more than a single episode of vomiting and/or diarrhea

The action should be to have the subject return to the Clinical Research Center the next day (Day 2) for dosing with the previous day's dose or the last tolerated dose (at the investigator's discretion) under observation. If the dose is tolerated, the subject will continue on that daily home dose for the normal time interval per protocol. If the subject does not tolerate this dose, the subject should receive the last tolerated dose (i.e., a 1-step

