dose reduction) or a 2-step dose reduction as their next day's dose (Day 3) in the Clinical Research Center. If this dose is tolerated, it will be continued as the daily home dose for the normal time interval, then escalation attempted in the Clinical Research Center as noted below. If this dose is not tolerated, then the next dose will be a further 1-2-step reduction in dosing (per investigator judgment), and the dose will be given in the Clinical Research Center (Day 4). If this next dose is not tolerated, then a discussion with the Medical Monitor will ensue to make a decision about whether to continue the subject on study-product treatment in the study.

If more *severe symptoms* occur, defined as:

- Skin severe generalized urticarial/angioedema/erythema
- Respiratory laryngeal edema, throat tightness with hoarseness, wheezing with dyspnea, stridor
- GI significant severe abdominal pain/cramping/repetitive vomiting and/or diarrhea
- Neurological change in mental status
- Circulatory clinically significant hypotension (see Appendix 3).

The action should be to treat the subject, and at the physician's discretion either 1) have them return to the Clinical Research Center the next day (Day 2) for dosing with a 2-step reduction in dose under observation or 2) discontinue them from the study product treatment. If the subject tolerates the dose reduction, then they will remain on that dose for 2 weeks and then return to the Clinical Research Center for the dose escalation. A discussion with the Medical Monitor may ensue to make a decision about whether to continue the subject on study product treatment in the study.

If a subject fails dose escalation after three consecutive attempts (with 2-4 weeks between), he/she will be considered an escalation failure and the last tolerated dose will be accepted as the maintenance dose (to Week 24). If the dose escalation is completed with no symptoms, subjects should be observed for 30 min. If the subject exhibits mild symptoms, the duration of the observation period should be 1-2 h post-protocol. For moderate to severe symptoms, the observation period should be at least 4 h and up to 24 h based on symptoms and the treatment regimen needed to stabilize the subject's condition.

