6.8.4 Reactions During Maintenance Phase

This phase consists of the subject receiving the maximum achieved daily dose of peanut OIT.

Subjects who fail escalation during the initial escalation period (Visit 1; Days 1 to 3), i.e., subjects who do not tolerate a minimum of 3 mg of study product (CPNA or matching placebo), will stop dosing and will not enter a maintenance phase. These subjects will be followed for safety and be asked to return to the Clinical Research Center 14 days following their last dose of study product to undergo an Early Discontinuation Visit (see, **Section 6.5**).

Subjects whose up-dosing is halted because of failing subsequent build-up (i.e., after the initial escalation period; Visit 1), will continue to be dosed at the last tolerated dose level and to be followed for safety biweekly (following their established visit schedule) until Week 24. The length of time from the cessation of up-dosing to Week 24 will constitute the maintenance phase for these subjects. The maintenance phase, thus, may vary in length from subject to subject. Dosing will be stopped after the Week 24 Visit; and the subject will be asked to return to the Clinical Research Center 14 days following their last dose of study product to undergo an Early Discontinuation Visit (see, Section 6.5).

There will be no maintenance phase for subjects who halt dose-escalation after Week 24. Dosing in these subjects will be discontinued when dose-escalation is stopped. They will be followed for safety and asked to return to the Clinical Research Center 14 days following their last dose of study product to undergo an Early Discontinuation Visit (see Section 6.5).

Subjects who achieve the targeted dose of 300 mg/d by Week 34 will then enter a 2-week maintenance phase. For these subjects, the maintenance phase will be followed by a DBPCFC performed at their Exit Visit (no later than week 36; see, Section 6.5).

All subjects will continue to follow a peanut-restricted diet for the duration of the study.

For any noted symptoms during the maintenance phase, the **same** study dosing rules for the build-up phase will be followed.

Figure 6–2. Schematic for Build Up Phase Dose Escalation – Day of Symptom

6.9 Missed Peanut OIT Doses at any Phase of the Study:

Missed Peanut OIT doses at any phase of the study can pose a significant risk to the enrolled subjects. The algorithm for missed consecutive doses of study product is as follows:

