- Miss 1 dose The next dose would be the current dose and could be given at home
- Miss 2 doses in a row The next dose would be the current dose and could be given at home
- Miss 3 doses in a row The next dose would be the current dose and would be given under observation (Clinical Research Center)
- Miss 4 doses in a row The next dose would be the current dose and would be given under observation (Clinical Research Center)
- Miss 5-7 doses in a row –Initiate the next dose as approximately 25% of the last tolerated dose. This would be done under observation (Clinical Research Center). Dose escalation would occur in the Clinical Research Center with an escalation no sooner than weekly and no longer than every 4 weeks with dose increases of 1-dose levels at each escalation. If symptoms occur, the dosing symptom rules in the build-up phase would apply
- Missing >7 consecutive days of therapy constitutes an individual stopping rule and the subject would no longer take the study product. The subject will be asked to return to the Clinical Research Center 14 days following their last dose of study product to undergo an Early Discontinuation Visit (see Section 6.5)
- Additionally; excessive missed doses, i.e., > 3 consecutive days missed on 3 occasions, constitutes an individual stopping rule and the subject would no longer take the study product. The subject will be asked to return to the Clinical Research Center 14 days following their last dose of study product to undergo an Early Discontinuation Visit (see Section 6.5).

No attempt should be made to make up for a missed dose if greater than 6 hours have elapsed since usual time of dosing.

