7.9.2 Individual Stopping Rules

Individuals may stop the study at any time if they experience subjectively intolerable adverse events or dosing symptoms. They must halt up-dosing and re-start with a reduced dose if more than three days of dosing are missed. Seven or more days of missed dosing constitutes an individual stopping rule, as does a significant number of episodes of missed dosing (ie, three or more days on at least three occasions). For additional individual stopping rules, the reader is referred back to Section 4.3.1.

Failure to accomplish up-dosing after three attempts will result in halting further updosing attempts, with the subject maintained at the previously achieved level. In addition, administration of two or more doses of epinephrine for the treatment of doserelated allergic reactions will result in halting further up-dosing attempts, with the subject maintained at the previously achieved level.

8. Mechanistic Assays

Complementary studies will be performed to measure humoral immune responses at baseline and at 6 months.

- Measurement of antigen-specific IgE and IgG4 levels
- SPT to peanut

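### The missed-dose rules in Protocol Sections 6.9 and 7.9.2 contradict each other at four missed doses, at seven missed days and on repeated gaps, and Section 6.8.2 cites the wrong section for them

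*Protocol*

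**What the plan says.** Study product is taken daily. Protocol Section 6.9 sets the restart after consecutive missed doses and opens with a warning: "Missed Peanut OIT doses at any phase of the study can pose a significant risk to the enrolled subjects". Its rules are:

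- One or two missed doses: the current dose, with home dosing permitted ("Miss 2 doses in a row The next dose would be the current dose and could be given at home").
- Three missed doses: the current dose, observed in the Clinical Research Center (CRC).
- Four missed doses: "Miss 4 doses in a row The next dose would be the current dose and would be given under observation (Clinical Research Center".
- Five to seven missed doses: about 25% of the last tolerated dose, observed in the CRC.
- More than seven consecutive days: the subject stops study product.
- More than three consecutive days on three occasions: the subject also stops.

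Section 7.9.2 covers the same ground differently: "They must halt up-dosing and re-start with a reduced dose if more than three days of dosing are missed". It stops the subject at seven or more missed days, or after three or more missed days on at least three occasions, and refers back to Section 4.3.1 for further rules. Section 4.3.1 uses more than seven consecutive days, and more than three consecutive days on three or more occasions.

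Section 6.8.2 lets the investigator withhold doses for an adverse event, whether or not it is treatment-related, and adds: "If doses are withheld for this, or any, reason, the rules for missed peanut OIT doses (Section 6.7) apply". Section 6.7 is the Physician Global Assessment. The missed-dose rules are in Section 6.9.

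**The concern.** The protocol itself treats missed doses as a significant risk, so the restart dose after a gap is a safety instruction. At four missed doses a site holds two instructions on the dose that cannot both be followed, and one of them is worded as mandatory. At seven missed days one section restarts the subject and the other removes the subject from study product. Sites could apply different rules to the same gap and each be able to cite the protocol.

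The thresholds also reach the analysis. A subject taken off study product before the exit food challenge counts as a non-responder under SAP Section 7.3 (unless the *ad libitum* peanut provision applies), so the choice of section can decide a subject's primary outcome.

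**Working it through.** The plan gives no figure to reproduce here. The check sets the two sections side by side by number of consecutive missed daily doses, then sizes the dose difference from the dosing schedule.

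| Consecutive daily doses missed | Section 6.9 | Section 7.9.2 | Result |
|---|---|---|---|
| 1–2 | current dose, home permitted | no rule | no conflict |
| 3 | current dose, CRC | no reduction required | no conflict on dose |
| 4 | current dose, CRC | reduced dose | **conflict** |
| 5–6 | about 25% of last tolerated dose, CRC | reduced dose | compatible |
| 7 | about 25% of last tolerated dose, CRC | stop | **conflict** |
| 8 or more | stop | stop | agree |

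Section 7.9.2 does not say that its more than three days are consecutive. Four doses missed in a row exceed three days on either reading, so the conflict does not depend on that point.

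Repeated gaps: a subject who misses exactly three consecutive days on three occasions continues under 6.9 and 4.3.1 (more than three days needed) and stops under 7.9.2 (three or more).

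Size at four missed doses. The home levels are 3 and 6 mg (Table 3-1), then 12, 20, 40, 80, 120, 160, 200, 240 and 300 mg (Table 3-2). The smallest reduction that satisfies 7.9.2 is one step, so the ratio is the current dose divided by the next lower level:

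- 6/3 = 2.0
- 12/6 = 2.0
- 20/12 = 1.67
- 40/20 = 2.0
- 80/40 = 2.0
- 120/80 = 1.5
- 160/120 = 1.33
- 200/160 = 1.25
- 240/200 = 1.2
- 300/240 = 1.25

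The range is 1.2 to 2.0. Equivalently, the next lower step is 50% to 83% of the current dose. At 3 mg there is no lower home level, so 7.9.2 cannot be applied there until a dose is named.

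Which rule fits the rest of the protocol? For temporary reductions during illness or menses, Section 6.8.2 allows the earlier dose to be resumed directly only if the reduction lasted three days or less; beyond that, re-escalation is observed in the CRC. Section 6.9 itself falls to about 25% one missed dose later. A full dose after four days with no dosing is the odd line out.

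**The case against.** The strongest reply is that 7.9.2 is a loose summary and 6.9 is the operative rule. On both stopping thresholds 4.3.1 agrees with 6.9, and 7.9.2 stands alone. Why then follow 7.9.2 at four missed doses? This stands in part: 4.3.1 is silent on the restart dose, so no third text settles it, and the documents do not show which rule was intended. The direction proposed below rests on the mandatory wording of 7.9.2 and the three-day limit in 6.8.2. It remains the sponsor's decision.

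It is also fair that 6.9 already requires CRC observation at four missed doses. The conflict concerns the dose, not the supervision. The wrong section number is a minor error, since the sentence names the missed-dose rules and only 6.9 carries that title.

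A reader might infer something stronger from the 6.8.2 sentence: that doses withheld after a moderate or severe reaction may be restarted at home, unobserved, after one or two days. The documents do not support that as a finding:

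- For moderate symptoms 6.8.2 says "The action should be to have the subject return to the Clinical Research Center the next day (Day 2) for dosing", under observation. For severe symptoms the choice is discontinuation or to "have them return to the Clinical Research Center the next day (Day 2) for dosing with a 2-step reduction in dose under observation".
- Section 6.8.2 also states that its symptom algorithm will be followed when moderate or greater symptoms are reported during home dosing.
- Section 6.8.3 sends the next dose to the CRC, reduced by one or two levels, when symptoms on a build-up day need more than two antihistamine doses or an antihistamine with another drug (epinephrine excepted). It sets a dose reduction after a single epinephrine administration in clinic. After epinephrine at home it calls for an observed clinic dose first.
- Home dosing in 6.9 is a permission, so a site that doses in the CRC meets both sections.
- The current dose is not defined for this case. Under Section 5.5 a subject whose dose is modified returns unused capsules "and be dispensed capsules at the adjusted dose level", so the current dose may already be the lower one.
- Figure 6-2, the day-of-symptom schematic, is not shown in the text available, and a precedence note there cannot be excluded.

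What remains is that neither 6.8.2 nor 6.9 states in words which governs when doses are withheld after a reaction. That justifies an optional clarifying sentence, no more.

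**Conclusion.** The point holds as a contradiction between safety rules. Sections 6.9 and 7.9.2 cannot both be followed after four missed doses, where the 6.9 dose is 1.2 to 2.0 times the next lower step for levels 6 to 300 mg. They also conflict at exactly seven missed days and on repeated gaps. The rules apply to all of the approximately 50 subjects in both arms. How many would meet one of these gaps cannot be estimated, because the documents give no rate of missed doses.

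The conclusion assumes one dose per day, as the schedule provides, and reads the halt to up-dosing in 7.9.2 as a pause rather than a permanent stop. The cross-reference to Section 6.7 is an error. The reaction rules themselves are not shown to be unsafe.

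**What to change.** 1. **Section 6.9, four missed doses.** Change the line to: *restart at least one dose level lower, under observation in the Clinical Research Center.* Name the restart dose for subjects at 3 mg, who have no lower home level.
2. **Stopping thresholds.** Use one stop threshold and one repeat-gap threshold in Sections 4.3.1, 6.9 and 7.9.2. Since 4.3.1 and 6.9 already agree, correcting 7.9.2 to more than seven consecutive days, and to more than three consecutive days on three or more occasions, is the smallest edit.
3. **Section 6.8.2.** Correct the reference from Section 6.7 to Section 6.9. Optionally add: *after a reaction to study product, Sections 6.8.2 and 6.8.3 take precedence over the home restart in Section 6.9.*

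The cost is a few lines in one amendment and no added patients. The CRC visit at four missed doses is already required.

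The real downside is time. Under Section 6.4.2 a subject whose dose is reduced holds the new dose for two weeks before escalating again. A subject stepped down from 300 to 240 mg at week *w* is back at 300 mg no earlier than *w* + 2, so Week 34 is met only if *w* ≤ 32. From 240 to 200 mg, two steps must be regained and the limit is *w* ≤ 30. SAP Section 3.2.2 puts an uncomplicated subject at 300 mg by about 18 or 20 weeks, which leaves 34 − 20 = 14 to 34 − 18 = 16 weeks of slack, so only subjects already delayed are exposed. For them a step-down could mean escalation failure and a non-response. With about 25 subjects per arm, each would-be responder lost this way moves that arm's response rate by 1/25 = 4 percentage points. How often this would occur cannot be estimated from the documents.

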Any subject deemed to have severe symptoms including hypoxia, hypotension, or change in mental status (stage 3 anaphylaxis defined in **Appendix 3**) or who receives aggressive therapy (to be determined by the investigator, but may include such interventions as IV epinephrine, intubation, or admission to an intensive care unit) for an allergic reaction at any time should be discussed with the Medical Monitor and discontinued from study product therapy.

For specific questions related to dosing escalation or continuation of the same dose that are not answered in the above protocol, the Medical Monitor will be available for questions.

Any subject who discontinues build-up dosing due to repeated allergic reactions to the characterized peanut allergen will have his/her mechanistic blood draw (refer to **Section 8**) within approximately 1 week of discontinuation of therapy.

6.8.3 Treatment for Reactions During the Build-up Phase: Pharmacological and Supportive Treatments

Treatment of individual reactions should be with either an antihistamine and/or epinephrine, along with IV fluids, a beta-agonist (e.g., albuterol, by inhaler or nebulizer), oxygen, and glucocorticosteroids, as indicated. Generally, for mild symptoms requiring treatment, the subject should receive antihistamines. Generally, for moderate symptoms requiring treatment, the subjects should receive antihistamines and/or epinephrine, as indicated. If severe anaphylaxis (stage 3 anaphylaxis defined in **Appendix 3**) occurs at any time, dose escalation will stop and the dose will be reduced to the last tolerated dose and the subject continued on that dose as long-term maintenance without further escalation.

Antihistamines

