If a subject receives antihistamines only, the dose escalation can be continued. If symptoms during a build-up day require antihistamines in multiple doses (>2) or in combination with other medications (except epinephrine), there should be a dose reduction by 1-2 doses with the next dose given in the CRC. If epinephrine is administered, then a different course of action is to be taken (see below). If dose escalation fails or requires treatment after two more escalation attempts, each spaced 2 to 4 weeks apart, the dose should be reduced to the last tolerated dose and continued long term (to Week 24) without further escalation. The subject will be followed for safety biweekly (following their established visit schedule) while continuing to be dosed at their last tolerated dose level until Week 24, i.e., a maintenance phase (see also Section 6.8.4). Dosing will be stopped after the Week 24 Visit; and the subject will be asked to return to the Clinical Research Center 14 days following their last dose of study product to undergo an Early Discontinuation Visit (see Section 6.5). For subjects who halt doseescalation after Week 24, there will be no maintenance phase. Dosing in these subjects will be discontinued when dose-escalation is stopped. They will be asked to return to the Clinical Research Center 14 days following their last dose of study product to undergo an Early Discontinuation Visit (see Section 6.5). No additional DBPCFC will be performed.

Epinephrine - General

Any reaction (in clinic or at home) that requires two or more doses of epinephrine will halt further dose escalation for this individual. Maintenance on the last tolerated dose is to be continued until Week 24. Dosing will be stopped after the Week 24 Visit; and the subject will be asked to return to the Clinical Research Center 14 days following their last dose of study product to undergo an Early Discontinuation Visit (see Section 6.5). For subjects who halt dose-escalation after Week 24, there will be no maintenance phase. Dosing in these subjects will be discontinued when dose-escalation is stopped. They will

be asked to return to the Clinical Research Center 14 days following their last dose of study product to undergo an Early Discontinuation Visit (see Section 6.5).

Epinephrine - Clinic

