7.5 Toxicity Grading

The study site assigns toxicity grades to indicate the severity of adverse experiences and toxicities. The CoFAR adopted usage of NCI-CTCAE v 4.0 for application in adverse event reporting and will likewise be used for this protocol. The allergic reactions in this protocol are defined beyond the NCI-CTCAE system, and include further characterization of anaphylaxis. Anaphylaxis is characterized as mild, moderate, or severe in **Appendix 3**, independent of the toxicity grade associated with the event. Toxicity grading for allergic reactions including anaphylaxis is modified from the NCI-CTCAE system to be more appropriate for this study population, and is displayed in **Table A4-2** in **Appendix 4**.

The NCI-CTCAE v 4.0 was specifically reviewed for this protocol and is appropriate for this study population. The purpose of using the NCI-CTCAE system is to provide standard language to describe toxicities and to facilitate tabulation and analysis of the data and assessment of the clinical significance of treatment-related toxicities.

The NCI-CTCAE provides a term and a grade that closely describes the adverse event. Each participating site will receive copies of the grading scales and event descriptions.

Record adverse events not included in the NCI-CTCAE listing and grade them 1 to 5 according to the General Grade Definition provided below:

Grade 1	Mild	Transient or mild discomforts (< 48 h), no or minimal medical intervention/therapy required, hospitalization not necessary (non-prescription or single-use prescription therapy may be employed to relieve symptoms, e.g., aspirin for simple headache, acetaminophen for post-surgical pain).
Grade 2	Moderate	Mild to moderate limitation in activity, some assistance may be needed; no or minimal intervention/therapy required, hospitalization possible.
Grade 3	Severe	Marked limitation in activity, some assistance usually required; medical intervention/therapy required, hospitalization possible.
Grade 4	Life-threatening	Extreme limitation in activity, significant assistance required; significant medical/therapy intervention required, hospitalization, or hospice care probable.
Grade 5	Death	Death

For additional information and a printable version of the NCI-CTCAE v. 4.03 manual, consult the NCI-CTCAE website, http://ctep.cancer.gov/reporting/ctc.html.

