Appendix 2: Evaluation of Asthma

The evaluation of asthma severity will be assessed using the NHLBI classification published August 28, 2007 as described in the table below.

Classification	Symptoms	Nighttime awakenings	Lung Function	Interference with normal activity	Short acting beta- agonist use
Intermittent (Step 1)	≤ 2 days per week	\leq 2x /month	Normal FEV ₁ between exacerbations FEV ₁ >80% predicted FEV ₁ /FVC normal*	None	≤2 days /week
Mild Persistent (Step 2)	> 2 days per week but not daily	3-4x /month	$FEV_1 \ge 80\%$ predicted FEV_1/FVC normal*	Minor limitation	>2 days /week but not >1x/day
Moderate Persistent (Step 3 or 4)	Daily	> 1x /week but not nightly	FEV ₁ ≥60% but <80% predicted FEV ₁ /FVC reduced 5%*	Some limitation	Daily
Severe Persistent (Step 5 or 6)	Throughout the day	Often 7x /week	FEV ₁ <60% predicted FEV ₁ /FVC reduced >5%*	Extremely limited	Several times per day

*Normal FEV1/FVC: 8-19 yr = 85%; 20-39 yrs = 80

Staging System of Severity of Anaphylaxis ²⁷			
Stage	Defined By		
1. Mild (skin & subcutaneous tissues, GI, &/or mild respiratory)	Flushing, urticaria, periorbital or facial angioedema; mild dyspnea, wheeze or upper respiratory symptoms; mild abdominal pain and/or emesis		
2. Moderate (mild symptoms + features suggesting moderate respiratory, cardiovascular or GI symptoms)	Marked dysphagia, hoarseness and/or stridor; shortness of breath, wheezing & retractions; crampy abdominal pain, recurrent vomiting and/or diarrhea; and/or mild dizziness		
3. Severe (hypoxia, hypotension, or neurological compromise)	Cyanosis or $\text{SpO}_2 \leq 92\%$ at any stage, hypotension, confusion, collapse, loss of consciousness; or incontinence		

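### After stage 3 anaphylaxis in build-up, Section 6.8.2 stops study product and Section 6.8.3 continues it; the Day 2 rule for severe symptoms at 6 mg also conflicts

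*Protocol*

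**What the plan says.** **Stage 3 anaphylaxis.** Appendix 3 defines stage 3 (severe) anaphylaxis by hypoxia, hypotension or neurological compromise; its signs include "hypotension, confusion, collapse, loss of consciousness; or incontinence". Two adjoining sections of the protocol act on that definition.

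- The end of Section 6.8.2 says that a subject with stage 3 anaphylaxis, or one given aggressive therapy, "for an allergic reaction at any time should be discussed with the Medical Monitor and discontinued from study product therapy".
- The opening of Section 6.8.3 says that if stage 3 anaphylaxis occurs at any time, escalation stops, "the dose will be reduced to the last tolerated dose and the subject continued on that dose as long-term maintenance without further escalation".

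Section 6.8.4 fixes how long the second order runs: "The length of time from the cessation of up-dosing to Week 24 will constitute the maintenance phase for these subjects". After that point the orders converge, because "There will be no maintenance phase for subjects who halt dose-escalation after Week 24" and dosing ends when escalation ends.

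**Day 2 at 6 mg.** The synopsis, Table 3-1 and SAP Section 3.2.2 send subjects with moderate or severe symptoms at 6 mg on Day 2 to a 3 mg dose on Day 3. Section 6.8.1 discontinues subjects with severe symptoms at any dose and classes them as escalation failures. Its summary allows one exception, for moderate symptoms confined to the 6 mg dose. Section 6.4.1 is mixed: its Day 1 text and Day 3 paragraph name moderate symptoms only, but its Day 2 bullet for 6.0 mg sets no severity limit.

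**The concern.** The first conflict arises after the most serious class of reaction short of death, in a trial that enrols children from age 4. One sentence withdraws the allergen and the other gives it daily for up to several months. A site can follow one and breach the other. The verbs make it worse: the protective order says should, while the order to continue says will.

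Neighbouring text also leans towards continuing. For severe symptoms in build-up, a list that includes change in mental status and clinically significant hypotension, Section 6.8.2 lets the physician choose "dosing with a 2-step reduction in dose under observation or 2) discontinue them from the study product treatment". Under Epinephrine - General in Section 6.8.3, "Any reaction (in clinic or at home) that requires two or more doses of epinephrine will halt further dose escalation for this individual", again with maintenance dosing to Week 24. Neither passage excludes stage 3 events.

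The second conflict is also about safety, and it can reach the endpoint for a rare subject. Under Section 6.8.1 a severe Day 2 reactor is a Visit 01 escalation failure and so a non-responder (SAP Table 7.2). Under Table 3-1 the same subject may go on to 300 mg and the exit challenge.

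**Working it through.** **1. Rules side by side**

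| Event | Rule | Action |
|---|---|---|
| Stage 3 anaphylaxis, build-up, at any time | End of 6.8.2 | Discuss with Medical Monitor and discontinue study product |
| Same event, phase and time scope | Opening of 6.8.3 | Stop escalation; continue at last tolerated dose |
| Severe symptoms, 6 mg, Day 2 | Synopsis, Table 3-1, SAP 3.2.2 | Return on Day 3 for 3 mg |
| Same | 6.8.1 | Discontinue; escalation failure |

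In each pair the trigger and phase match and the actions cannot both be followed. Section 3.2 defines the initial escalation period as Visit 1, Days 1 to 3, so Section 6.8.1 governs Day 2. The Day 2 conflict is confined to severe symptoms; moderate symptoms at 6 mg are handled the same way throughout.

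**2. Extra exposure under Section 6.8.3, per affected subject**

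Inputs: up-dosing every 2 weeks (Table 3-2), a 6 mg start, no earlier reductions, a reaction at the scheduled Week *w* step, maintenance at the previous dose to Week 24 (Section 6.8.4), and no discretionary stop. Further doses = (24 − *w*) × 7. Under the Section 6.8.2 order the figure is 0.

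| Week *w* step | Dose reacted to | Dose held | Doses to Week 24 | Peanut protein |
|---|---|---|---|---|
| 2 | 12 mg | 6 mg | 22 × 7 = 154 | 154 × 6 = 924 mg |
| 12 | 160 mg | 120 mg | 12 × 7 = 84 | 84 × 120 = 10,080 mg |
| 14 | 200 mg | 160 mg | 10 × 7 = 70 | 70 × 160 = 11,200 mg |
| 18 | 300 mg | 240 mg | 6 × 7 = 42 | 42 × 240 = 10,080 mg |

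**3. How often**

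The documents give no rate for stage 3 anaphylaxis in build-up. Section 1.6.1 expects severe symptoms of any kind during dosing in under 1% of subjects. With about 25 subjects on CPNA:

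- Expected subjects with any severe symptom: below 25 × 0.01 = 0.25.
- If every one were stage 3, the chance of at least one case is below 1 − 0.99^25 = 22%. This is the only ceiling the documents support.
- If 10% to 50% of them are stage 3 (an assumption), the expected count is below 25 × 0.001 = 0.025 to 25 × 0.005 = 0.125. The chance of at least one case is then below 1 − 0.999^25 = 2.5% to 1 − 0.995^25 = 12%.

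**4. Effect on the primary endpoint**

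Both stage 3 orders stop escalation, so a subject below 300 mg is normally a non-responder either way. For the Day 2 conflict, one reclassified CPNA subject would move that arm's response rate by 1/25 = 4 percentage points. Severe Day 2 reactors are a subset of the same under-1% group.

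**The case against.** The best reply on stage 3 is that other text already points to discontinuation. Section 4.3.1, item 1, lists anaphylaxis with hypotension or neurological compromise, close to the Appendix 3 wording, and Section 7.9.2 refers to that list as further individual stopping rules. The lean is real, but it does not settle the matter. Section 4.3.1 says such subjects may be terminated, and it is keyed to CoFAR grades, while Section 7.5 makes anaphylaxis stage "independent of the toxicity grade associated with the event".

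Medical Monitor discussion, 24-hour anaphylaxis reporting, and study suspension after a treatment-associated death or a second dosing-related hospital admission (Section 7.9.1) all reduce the risk. None says which order applies to the subject at hand. The closing sentence of Section 6.8.2 requires discussion and discontinuation, not a discussion about whether to discontinue.

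On Day 2, the reply is stronger. Only a subject who tolerated 6 mg on Day 1 receives 6 mg on Day 2. To change responder status, that subject must then react severely, be re-dosed, tolerate 3 mg, reach 300 mg and pass the exit challenge. The 4-point figure is not weighted for that chain. SAP Sections 7.3 and 7.4 classify subjects by what happened, so conduct is ambiguous and the analysis rule is not. This part alone is a wording alignment.

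Two limits stand. Figures 6-1 and 6-2 are not available, so they may show which rule sites were directed to follow, although a figure could not remove the conflicting text. The SAP addendum of 10 February 2015 describes post-exit dosing in the past tense, so some subjects had already finished and an amendment could protect only those still dosing.

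**Conclusion.** Both contradictions hold on the text, and nothing in the documents reconciles either pair.

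The stage 3 conflict must be fixed, on grounds of participant safety. It is the difference between no further allergen and up to 11,200 mg in the cases tabulated, and it matters before Week 24. The dose figures are upper values that rest on the conditions listed with them. The event is unlikely in a trial of this size: below 22% for at least one case in the CPNA arm on the protocol's own expectation, and below 2.5% to 12% if 10% to 50% of severe cases are stage 3. Rarity does not excuse the gap, since the rule exists for the rare case.

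The Day 2 conflict is a lesser matter of wording. Neither part materially affects the primary analysis or the power statement.

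**What to change.** 1. Make discontinuation of study product, with Medical Monitor discussion, the single rule for stage 3 anaphylaxis. Replace the continue-on-maintenance sentence in Section 6.8.3 with a reference to the closing rule of Section 6.8.2.
2. State that the re-dosing option for severe symptoms in Section 6.8.2 and the epinephrine rules in Section 6.8.3 do not apply to stage 3 anaphylaxis.
3. Remove severe symptoms from the Day 2 rule at 6 mg in the synopsis, Table 3-1 and SAP Section 3.2.2. Limit the Day 2 bullet for 6.0 mg in Section 6.4.1 to moderate symptoms, with severe symptoms leading to discontinuation under Section 6.8.1.
4. Check that Figures 6-1 and 6-2 agree. Check the ARC002 protocol too, since Section 3.4 gives its former placebo subjects the same escalation schedule.

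The cost is a short amendment with sponsor, DMC and IRB approval and FDA submission (Section 11.1), a site memo and one changed SAP sentence. No extra subjects or procedures are needed. The downside is that a rare subject who might have continued dosing would be withdrawn.
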